## 10. SAFETY

### 10.1 Definition and assessment of (serious) adverse events and other safety related events

As the intervention trialled in this study is not specific to a single drug or drug class, no specific Adverse Events (AEs) can be predicted: potential AEs depend on the drugs having been stopped and the participant's health status.

Adverse Events will thus be defined as any unfavourable and unintended sign, symptom, or disease for which a causal relationship with the intervention cannot be excluded.

Serious Adverse Events are defined as AEs that:

- result in death,
- are life-threatening,
- require in-patient hospitalization, or
- result in persistent or significant disability/incapacity.

SAEs will be followed by the NH team until resolution.

#### 10.1.1 Assessment of Causality

Causality will be assessed by the Investigators, based on the criteria listed in the ICH E2A guidelines:

| Relationship | Description  |
|--------------|--|
| Definitely   | Temporal relationship
Improvement after reintroduction of suspected drug
Recurrence after new withdrawal |
| Probably     | Temporal relationship
Improvement after reintroduction of suspected drug
No other cause evident          |
| Possibly     | Temporal relationship
Other cause possible  |
| Unlikely     | Any assessable reaction that does not fulfil the above conditions  |
| Not related  | Causal relationship can be ruled out   |

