# **8. STUDY INTERVENTION**

## **8.1 Identity of Investigational Intervention**

### **8.1.1 Experimental Intervention**

The intervention tested in this study is a medication review focused on deprescribing, followed by the construction and implementation of a deprescribing plan. A medication review is "a structured evaluation of a patient's medicines with the aim of optimising medicines use and improving health outcomes." [48] This review will take into account the clinical situation of the participant, including pathologies, disabilities, current drug regimen, and her / his therapeutic and life goals.

The responsible pharmacist of the NH where the participant resides will perform the medication review. They will receive education on the realisation of medication review prior to the study by attending the "Medication review" module of the Certificate in Advanced Studies "Pharmacie Clinique: prestations dans les soins de base" . Through the study, pharmacists will be able to solicit the clinical advices of the *Centre de Pharmacie Communautaire* Pharmaceutical Assistance team for performing of the reviews.

The results of the review will be structured propositions of drug regimen modification, according to the clinical situation of participant and the risk/benefit balance of each prescribed drug for her-/him-self. These propositions will include regimen modifications (modification of galenic forms or administration time or frequency), withdrawal or tapering of non-beneficial drugs (deprescribing), and introduction of new drugs in case of prescribing omission (sub-optimal treatment). These propositions will be discussed with nurse and treating physician of the NH, with the goal to create a deprescribing plan that will be proposed to the participant. The propositions resulting from the review and the deprescribing plan will be prepared following the model documents in Annex 8.

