## **10.2 Reporting of serious adverse events (SAE) and other safety related events**

### **10.2.1 Reporting of SAEs**

All SAEs will be reported to the investigators within a week of occurrence by the study nurse, using a specific CRF (see Annex 16). The investigators will contact the NH care team to discuss in details the situation. If necessary, the advice of a geriatrician ([name], CHUV) will be solicited by the investigators for the discussion of the SAE with the NH care team. For the cases where a causal link with the intervention remains probable or definitive after investigation, the CER-VD will be informed within 24 hours via BASEC. In all cases, reported SAEs will be reported to the CER within 15 days via BASEC.

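### As written, the causality scale in 10.1.1 does not let deaths, events not reversed by reintroduction, or reactions to added drugs reach the two grades that match the 24-hour notice

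*Combined protocol and SAP*

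**What the plan says.** Section 10.1.1 has the investigators grade causality from a five-row table.

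- *Definitely*: temporal relationship; "Improvement after reintroduction of suspected drug"; "Recurrence after new withdrawal".
- *Probably*: temporal relationship; the same reintroduction line; "No other cause evident".
- *Possibly*: temporal relationship; "Other cause possible".
- *Unlikely*: "Any assessable reaction that does not fulfil the above conditions".
- *Not related*: a causal link can be ruled out.

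Section 10.1 defines adverse events against the intervention as a whole. Its criteria for a serious event begin with those that "result in death" and include persistent disability. The intervention is not limited to withdrawals: section 8.1.1 also provides for regimen changes and for "introduction of new drugs in case of prescribing omission (sub-optimal treatment"). Section 6.1 repeats that the plan may add drugs, and section 5.2 counts new drugs as secondary outcome 4.

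Section 10.2.1 sets the reporting times. The faster route reads: "For the cases where a causal link with the intervention remains probable or definitive after investigation, the CER-VD will be informed within 24 hours via" (the quotation stops before the name of the submission system). Every reported SAE, whatever its grade, goes to the committee within 15 days.

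**The concern.** The table is built for one pattern: a drug is withdrawn, a reaction follows, the drug is restarted and the reaction resolves. That pattern is sound evidence of causality when it occurs, but here it is a condition for both upper grades, and several of the events that matter most cannot show it. A death cannot improve. Persistent disability may not. Restarting a drug is allowed at any time (7.4) but is not required, so a reaction may be managed without it. A reaction to an added drug has no withdrawn drug to restart.

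The lower grades do not catch these events properly either. *Possibly* needs a competing cause, so an event with good timing and no rival explanation has no natural place above *Unlikely*.

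Two things are at stake: a correct causality grade for serious events in a trial of drug withdrawal in frail residents, and the faster of the two routes to the ethics committee. There is no data safety monitoring committee (1.6) and no interim safety report (10.2.5), so the reporting rule should work as its text suggests.

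**Working it through.** The plan gives no figure to reproduce. The check is to read each row against each kind of event.

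**Are the lines in a row joint or alternative?** The table does not say. Three features point to joint. *Definitely* and *Probably* share their first two lines and differ only in the third. If the lines were alternatives, a temporal relationship alone would satisfy three grades at once. And *Unlikely* takes whatever fails the conditions above it. I read them as joint.

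**Applying the rows.** Each event has a temporal relationship and, unless stated, no other evident cause.

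| Event | *Definitely* | *Probably* | *Possibly* | Literal grade |
|---|---|---|---|---|
| Reversible withdrawal reaction, drug restarted, improvement seen | only if it also recurs on new withdrawal | met | not needed | *Probably* or *Definitely* |
| Same kind of reaction, drug not restarted | fails | fails | fails | *Unlikely* |
| Death, no prior improvement on reintroduction | fails | fails | fails | *Unlikely* |
| Irreversible event, no improvement | fails | fails | fails | *Unlikely* |
| Reaction to a drug added under the plan | fails | fails | fails | *Unlikely* |
| The same death, but another cause is possible | fails | fails | met | *Possibly* |

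The failures under *Definitely* and *Probably* come from the reintroduction line. For an added drug, the recurrence line also runs the wrong way: a reaction to a new drug would be expected to resolve on stopping that drug and to return on restarting it. The failures under *Possibly* come from the competing-cause line. Comparing the third and last rows, the event with the stronger case for causality gets the lower grade.

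**Mapping to reporting.** Only the first row reaches a grade matching the 24-hour rule in 10.2.1. The other five go by the 15-day route. No other section gives a substitute criterion.

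**Scale of deaths (illustrative).** Inputs: 106 expected participants (11.2); 1:1 allocation (6.2.1); mean stay under 3 years in the homes of the two cantons (3.4); 4 months of follow-up (5.1). Assumptions: exponential survival, a mean of 36 months, and every stay ended by death.

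- Proportion dying in 4 months: 1 − exp(−4/36) = 0.105, or 10.5%.
- Intervention arm: 106/2 = 53; 53 × 0.105 = 5.6, so about 5 to 6 deaths.

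Since 3 years is an upper limit on the stated mean stay, a shorter mean gives more deaths under the same assumptions; stays that end other than by death would give fewer. The figure counts all deaths in the arm. Only those with a temporal link and no other evident cause would change grade under the fix, and the documents give nothing from which to estimate that share.

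**The case against.** The strongest reply is that the table guides judgement. Section 10.1.1 has causality assessed on the basis of the criteria and does not state that every line is required. The perverse ordering produced by a strict reading is itself a sign that strictness may not have been meant. A participant could improve for a time on reintroduction and later die, and an irreversible event could partly improve. An investigator might also hold that some other cause is nearly always possible in this population and use *Possibly*. This stands in part: a reader might infer that no fatal event can ever be graded probable, and the documents do not support that absolute. But relying on investigators to set the table aside concedes that the table does not work for these events, and *Possibly* still falls short of the 24-hour trigger.

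Second, 10.2.1 does not cite 10.1.1 and uses slightly different words, and the link is judged after investigation, with a geriatrician's advice if needed. So the tie between grade and trigger is an inference. It is the natural one, since the trigger's terms correspond to the top two grades and no other scale is given.

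Third, the delay should not be stated as a move from 24 hours to 15 days. The nurse has up to a week to report, investigation follows, and neither period has a stated starting point. The actual difference is undefined.

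Fourth, a reader might infer that the 24-hour notice is the trial's only early safety signal, or that its final safety results would be distorted. Neither follows. SAEs reach the investigators within a week and prompt contact with the care team. An independent monitor follows activity weekly and checks on site that adverse events are reported in a timely way (12.3). The sponsor-investigator may stop the study if homes raise safety concerns (2.9). No table of causality grades is planned, and the comparisons in 11.4.6 count events by arm regardless of grade.

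**Conclusion.** The point holds as a defect in a written rule. With the lines read jointly, a death or irreversible event without prior improvement on reintroduction, an event where the drug was not restarted, and a reaction to an added drug all miss the upper two grades. Where no other cause is evident they fall to *Unlikely*, below the same event with a competing cause. By default they then miss the 24-hour notice and reach the committee by the 15-day route.

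The size is limited. No SAE goes unreported for this reason, and neither the primary analysis nor the between-arm safety comparisons are touched. The number of events affected cannot be derived. A reader might take expected deaths across all 106 participants, about 11 (106 × 0.105), as the measure. That counts both arms and includes deaths that no revised scale would regrade. About 5 to 6 intervention-arm deaths, on the survival assumptions above, is only the pool from which affected deaths would come; non-fatal events would add to it by an unknown number.

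The conclusion rests on the joint reading and on the trigger in 10.2.1 using the grades in 10.1.1. Whether the table matches the guideline it cites was not checked and plays no part. The correction is worth making before the first inclusion.

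**What to change.** Amend the table in 10.1.1:

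- *Probably*: a temporal relationship and no other evident cause. Improvement after the change is reversed counts as supporting evidence, only where reversal was possible and was done.
- *Definitely*: keep the rechallenge pattern.
- All rows: word the criteria for any change made under the deprescribing plan (withdrawal, taper, regimen change or added drug), so that reversal means undoing whichever change was made.

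Align the SAE form (Annex 16) if it repeats the criteria; the form is listed but could not be seen. Leave the 24-hour trigger in 10.2.1 and all clinical care as they are. The change affects grading and reporting only.

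The cost is the rewording of one table and possibly one form. The downside is that a few more events may need 24-hour notice.

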#### 10.1.2 Unexpected Adverse Drug Reaction

Not applicable to this study.

#### 10.1.3 Suspected Unexpected Serious Adverse Reactions (SUSARs)

Not applicable to this study.

#### 10.1.4 Assessment of Severity

The severity of SAEs will be graded using the definition of the Common Terminology Criteria for Adverse Events (CTCAE) v 5.0 [49]. The gradation is implemented in the REDCap CRF for collection of SAEs (Annex 16).

 Given the population and setting of the study, congenital anomalies or birth defects are implausible.

## **10.2 Reporting of serious adverse events (SAE) and other safety related events**

### **10.2.1 Reporting of SAEs**

All SAEs will be reported to the investigators within a week of occurrence by the study nurse, using a specific CRF (see Annex 16). The investigators will contact the NH care team to discuss in details the situation. If necessary, the advice of a geriatrician ([name], CHUV) will be solicited by the investigators for the discussion of the SAE with the NH care team. For the cases where a causal link with the intervention remains probable or definitive after investigation, the CER-VD will be informed within 24 hours via BASEC. In all cases, reported SAEs will be reported to the CER within 15 days via BASEC.

### **10.2.2 Reporting of SUSARs**

Not applicable to this study.

### **10.2.3 Reporting of Safety Signals**

Not applicable to this study.

### **10.2.4 Reporting and Handling of Pregnancies**

Not applicable to this study, as all participants must be 65 years old or more.

### **10.2.5 Periodic reporting of safety**

As the duration of this study is less than a year, no interim safety reports will be submitted. Safety will be assessed in the final report to the EC.

## **10.3 Follow up of Serious Adverse Events**

All participants with ongoing SAEs at the end of the study will be followed by the NH team.

## 11. STATISTICAL METHODS

### 11.1 Hypothesis

The null hypothesis ( $H_0$ ) is that the intervention has no effect on the use on PIMs by NH residents. The alternate hypothesis ( $H_1$ ) is that the intervention has an effect.

### 11.2 Determination of Sample Size

No data on the repartition of the number of PIMs used by NH residents in Vaud and Fribourg are available prior to the study. This, no power calculation can or determination of the sample size needed can be made in advance.

We anticipate that half of the 18 eligible NH will agree to take part in the study; with a mean number of beds of 59 in these NHs, the recruitment of 20% of the population should lead to the inclusion of 106 residents.

### 11.3 Statistical criteria of termination of trial

As no interim analyses are planned, no criteria for the discontinuation of the trial have been set.

### 11.4 Planned Analyses

#### 11.4.1 Datasets to be analysed, analysis populations

The analyses will be performed following the intention to treat approach.

#### 11.4.2 Descriptive statistics

The participants will be described, by group, in terms of age, gender, and length of stay in the NH at inclusion. Their drug regimen at baseline and follow-up will be described in terms of number of regular treatments, classified according to the Anatomical Therapeutic Chemical classification. Drugs withdrawn or added as a result of the intervention will be described in the same way.

Implementation outcomes will be analysed in descriptive terms only; no statistical tests will be performed on these data.

#### 11.4.3 Primary Analysis

The comparison of the primary outcome (change in number of PIMs between baseline and 4 months) between groups will be performed by means of generalised linear mixed models (GLMM), with patient representing a random effect clustered within NH and the allocation group as a fixed effect.

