### **5. STUDY OUTCOMES**

#### **5.1 Primary Outcome**

The primary endpoint of the study is the change in the number of PIMs prescribed to participants between baseline and 4 months. It was chosen because the main effect of the intervention will be to reduce the number of inappropriate medications prescribed to participants.

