#### **5.2 Secondary Outcomes**

Secondary outcomes are:

1. The change between baseline and 4 months in the number of potentially inappropriate Defined Daily Doses (DDDs) prescribed to participants;
2. The change between baseline and 4 months in the number of regular drugs prescribed to participants;
3. The change between baseline and 4 months in the number of regular DDDs prescribed to participants;
4. The number of new drugs prescribed as a result of the intervention;
5. The change in health-related quality of life between baseline and follow-up, measured with EQ-5D-5L [40] (see Annex 4 for the questionnaires);
6. The change in the number of common drug-related complaints presented by the participant between baseline and follow-up (see Annex 5 for the questionnaire on common complaints);

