After randomisation, the record of participants allocated to the intervention group will be searched by the nurse responsible for the study in the NH ("study nurse") for clearly stated objectives of care. If no objectives are present in the record, the referent nurse for this participant will be interviewed by the pharmacist to clarify these objectives. The referent nurse will also provide a list of drugs taken by the participant without supervision of the NH staff (self-medication). Using this information and the content of the participant's records in the NH and in the pharmacy, the pharmacist will then conduct the medication review according to the formation received; the medication review process is described in chapter 8, page 20. Based on the results of the medication review, a deprescribing plan will be decided by the NH care team (head nurse, physician(s) responsible for the resident(s), and pharmacist). This plan will also include proposition for the introduction of new drugs if prescription omissions (sub-optimal treatment) are detected by the medication review. Each item of this plan will then be presented for validation to the participant or her/his representative. Once validated, baseline data collection will occur and the deprescribing plan will be implemented.

Participants allocated to the control group will receive usual care. Baseline data collection for them will occur after inclusion. Follow up data collection will occur 4 months after baseline data collection for both groups. The duration of the study will be 4 months for the participants allocated to the control group. For participants allocated to the intervention group, the realisation of the medication review by the pharmacist, the discussion of its results with the treating physicians, the creation of the deprescribing plan, and its discussion with the participant will induce a delay before baseline data collection, estimated of maximum 2 months; thus, the total duration of the study could be up to 6 months in this group. Participants allocated to both groups will be monitored as usual by the NH care team (treating physician and nurses) during and after the duration of the study. In addition, the NH care team will mention specific monitoring measures in the deprescribing plan, according to the drugs being deprescribed and the clinical situation of the participant.

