### **9.2 Assessments of outcomes**

#### **9.2.1 Assessment of primary outcome**

The primary outcome is the change in the number of PIMs between baseline and 4 months. To identify PIMs, NH pharmacists will use the online implementation of the STOPP/START tool provided by the French *Caisse Nationale d'Assurance Maladie*, found at <https://aide-a-la-decision.ameli.fr/revision-ordonnance/>. This tool requires the pharmacist to enter the patients' pathologies and treatments, but no other information. No information are stored on the website once the analysis has been performed. An example of such analysis can be found in Annex 9.

The pharmacist will then upload the PIM report and the participants' treatment plan into the CRF (see Annex 10). The investigators will then transcribe the medication plan for each participant into an investigator-reserved CRF (see Annex 11), including the PIM status of each treatment. This analysis will be made at baseline and 4 months.

The total number of PIMs at every time point for each participant will then be computed by the investigators, and difference in the number of PIMs between baseline and follow-up computed for each participant.

---

 Authorisation for the use of this tool has been granted by its co-concepteur, [name].

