### 9.3.1 Visit 1: Baseline data collection

Timeframe: immediately after inclusion for control group; at the time of implementation of the deprescribing plan for the intervention group.

Action performed with the participant:

- Completion of the baseline EQ-5D-5L questionnaire (using the paper version), by the pharmacist and the nurse, in presence of the participant or her/his representative;
- Completion of the baseline common complaints questionnaire (see Annex 5);
- Planning of the follow-up visit.

Action performed after the visit, in the absence of the participant:

- Upload of the baseline EQ-5D-5L questionnaire into the CRF;
- Upload of the baseline common complaints questionnaire into the CRF;
- Upload of the current medication plan into the CRF;
- Performing and upload of the PIM assessment, as described in section 9.2.1;
- Upload of the deprescribing plan (see Annex 8) into the CRF;
- Completion of the NPI-NH questionnaire (see Annex 6) by the nurse referent for the participant, and upload by the pharmacist into the CRF.

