#### 11.4.4 Secondary Analyses

The same GLMM models as for the primary outcomes will also be used to compare all patient-level secondary outcomes between the intervention groups. NH-level outcomes will be compared between allocation groups by mean of t-tests if the outcomes follow a normal distribution, by means of Mann-Whitney otherwise.

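### The primary model uses the baseline PIM count only by subtraction, which gives up precision in a trial of about 106 residents

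*Combined protocol and SAP*

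**What the plan says.** Section 5.1 defines the endpoint: "The primary endpoint of the study is the change in the number of PIMs prescribed to participants between baseline and 4 months". Section 9.2.1 has the PIM count assessed at both visits and the "difference in the number of PIMs between baseline and follow-up computed for each participant", so each participant contributes one change value.

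Section 11.4.3 compares that value between arms with a generalised linear mixed model, "with patient representing a random effect clustered within NH and the allocation group as a fixed effect". Allocation is the only fixed effect named. No section mentions the baseline PIM count, or anything else, as a covariate, and no distribution family or link is given.

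Section 11.4.4 extends the specification: "The same GLMM models as for the primary outcomes will also be used to compare all patient-level secondary outcomes between the intervention groups". Section 11.2 gives no power calculation. It expects that "the recruitment of 20% of the population should lead to the inclusion of 106 residents".

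On the timing of baseline, section 9.3.1 says: "Timeframe: immediately after inclusion for control group; at the time of implementation of the deprescribing plan for the intervention group".

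**The concern.** Subtracting baseline fixes its slope at 1. If the true slope of the 4-month count on the baseline count differs from 1, the change score still carries variation that baseline could explain, and the standard error of the arm difference is larger than it need be.

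A slope below 1 is plausible here. Section 7.1 requires five or more regular drugs but no minimum number of PIMs, and nobody can lose more PIMs than they start with, so the possible fall depends on the starting count.

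The size of the trial comes from feasibility and not from a precision target. Recruitment stops at 20% of each home (7.2) and withdrawals are not replaced (7.4). Analysis efficiency is therefore one of the few ways left to gain precision. What is at stake is power and interval width, not the validity of the test.

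There is also a wording problem. In a Gaussian model with one value per participant, a patient random effect cannot be separated from the residual. It does not materially change the estimate or its standard error, but the text leaves the fitted model unclear.

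**Working it through.** **Expected size.** From section 11.2: half of 18 homes, 59 beds on average, 20% recruited. (18/2) × 59 × 0.20 = 106.2, which reproduces the stated 106. Section 6.1 uses 10 × 50 × 0.20 = 100. The conclusion is the same at either figure.

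**Inputs the documents do not give.** The correlation ρ between the two PIM counts and their SDs are not stated. I take ρ from 0.3 to 0.9, first with equal SDs (s), and n = 106 split 1:1.

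**Formulas.**
- Change score: variance 2s²(1−ρ)
- Baseline-adjusted: variance s²(1−ρ²)
- Ratio: (1+ρ)/2
- SE of the arm difference: residual SD × √(4/106) = residual SD × 0.194
- Finite-sample cost of one covariate: (106−3)/(106−4) = 1.0098, about 1% in variance

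Results with s = 1. The equivalent N is 106 divided by the ratio.

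| ρ | Var, change | Var, adjusted | Ratio | Ratio with covariate cost | SE, change | SE, adjusted | Equivalent N |
|---|---|---|---|---|---|---|---|
| 0.3 | 1.40 | 0.91 | 0.65 | 0.66 | 0.230 | 0.185 | 163 |
| 0.5 | 1.00 | 0.75 | 0.75 | 0.76 | 0.194 | 0.168 | 141 |
| 0.7 | 0.60 | 0.51 | 0.85 | 0.86 | 0.150 | 0.139 | 125 |
| 0.9 | 0.20 | 0.19 | 0.95 | 0.96 | 0.087 | 0.085 | 112 |

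Assuming two-sided 5% (no level is stated) and no dropout, an effect that the change score detects with 80% power is detected by the adjusted model with 93.5%, 89.9%, 86.0% and 82.0% power.

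**Unequal SDs.** With k = follow-up SD / baseline SD, the ratio is k²(1−ρ²)/(1+k²−2ρk). The excess variance of the change score is (s₀ − ρs₁)², where s₀ and s₁ are the baseline and follow-up SDs. It is never negative and is zero only when the slope ρk equals 1.
- k = 0.8: 0.50, 0.57, 0.63, 0.61 for ρ = 0.3, 0.5, 0.7, 0.9
- k = 1.1: 0.71, 0.82, 0.92, 1.00. At ρ = 0.9 the slope is 0.99, so there is no gain.

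**Check on counts.** PIM counts were simulated with an assumed baseline mean of 3, 106 residents in 10 homes and a random home intercept. With no treatment effect, the variance ratios were 0.613, 0.715, 0.844 and 0.972 at ρ of about 0.47, 0.68, 0.85 and 0.97. Both models gave the same mean effect when baselines were comparable (for example −0.279 and −0.281). A second simulation with 9 homes gave an SE of 0.233 for the change score and 0.206 adjusted, a variance ratio of 0.206²/0.233² = 0.78.

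**Late baseline.** If early changes have already shifted the intervention-arm baseline by d, the change score misses d of the effect since randomisation and the adjusted model misses slope × d. Suppose 10% of intervention-arm PIMs (about 0.30) are already withdrawn at Visit 1. Simulation then gives an effect since randomisation of −0.42, a change-score estimate of −0.42 + 0.30 = −0.12, and an adjusted estimate of −0.25.

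**The case against.** **The plan contains no error.** A change endpoint compared between randomised arms is coherent and valid, and adjustment is good practice rather than an obligation. This stands, and the point is made as lost efficiency only.

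**The size is assumed.** It runs from about half the variance saved to nothing. The no-effect simulations also imply a follow-up SD of about 0.85 to 0.99 of baseline, which favours adjustment. Both statements are correct. The simulations support the direction, and the closed-form range is the figure to rely on.

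**The sample size is not strictly fixed.** The 106 is a forecast. All 18 homes would give 18 × 59 × 0.20 = 212, and the 20% cap is a design choice. True, but the variance ratio does not depend on n, so the loss would persist.

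**The model might be a repeated-measures one.** A patient random effect is natural with two counts per patient. However, 11.4.3 names the change as the outcome and gives no time or group-by-time term. With complete data, an unconstrained linear version returns the same contrast as the change score. Only a model constraining the arms' baseline means to be equal would recover the precision, and none is stated.

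**The covariate is not a clean baseline.** This is the strongest objection. In the intervention arm Visit 1 follows randomisation by up to two months, so the two analyses could differ in estimate as well as precision. Section 6.1 does place the measurement before the changes ("Once validated, baseline data collection will occur and the deprescribing plan will be implemented"), and no figure supports any particular amount of early withdrawal. The planned change score relies on the same value at full weight, so with a slope between 0 and 1 it is harmed more. Baseline timing is a real problem, but no reason to keep the unadjusted model.

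**Conclusion.** The concern holds. The plan collects the baseline PIM count and then uses it only by subtraction. Where the arms have comparable baselines, adjusting for it estimates the same arm difference and, in large samples, is never less precise. With equal SDs the variance saved is 35%, 25%, 15% or 5% at ρ = 0.3, 0.5, 0.7 or 0.9. It is 37% to 50% if the follow-up SD is 0.8 of baseline, and 29% down to nil if it is 1.1 times baseline. The worst case is a cost of about 1% in variance.

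The omission and the direction are certain. The size rests on an assumed ρ and SD ratio, and on a linear model. This should be changed, but it does not invalidate the planned test.

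**What to change.** In section 11.4.3, specify a linear mixed model (Gaussian, identity link) for the 4-month PIM count, with allocation and Visit 1 PIM count as fixed effects and a random nursing-home intercept. Drop the patient term. In this linear model, using the change as response gives the identical treatment estimate and SE, so the endpoint is unaltered. In one simulated dataset both gave an SE of 0.2781, against 0.3227 for the unadjusted change. If a count family is preferred, name it and its link. The effect scale then differs and the ratios above need not apply.

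In section 11.4.4, use the same form for both DDD outcomes, the number of regular drugs, EQ-5D-5L and complaints, each with its own baseline. Exclude outcomes that have none, such as "The number of new drugs prescribed as a result of the intervention".

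State as a limitation that the intervention-arm baseline is recorded after randomisation and that adjustment does not remove this. If the timing is corrected, use a PIM count from before allocation. The regular-drug count used for ranking (7.2) may be added but should not replace baseline PIMs. With equal SDs and the 4-month count as response, that replacement beats the change score only if its correlation r with the 4-month PIM count satisfies r² > 2ρ−1, that is r > 0.63 at ρ = 0.7 or r > 0.89 at ρ = 0.9.

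The cost is analysis wording only, ideally settled before database lock. Moving the baseline ahead of allocation would change visit procedures. It is a separate matter and not a condition of this fix.
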